1.0 ABSTRACT

This is an investigator initiated randomized controlled trial (RCT) of two ablation protocols that are currently done in our EP lab, but have not been studied prospectively to identify which, if either, is superior for patients with persistent atrial fibrillation. Specifically, we would like to perform a RCT of 100 patients who will be consecutively enrolled and randomized to either *Arm 1* (PVI) or *Arm 2* (PVI+PI). PVI=pulmonary vein isolation. PI=posterior wall isolation.

Expected Outcomes

Primary study outcome is the percentage of patients free from atrial arrhythmias and off AADs at 1 year after single ablation procedures.

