3.0 OBJECTIVES/STUDY AIMS

The objective of this RCT is to compare 2 ablation strategies, PVI alone and PVI plus posterior wall isolation, in patients with persistent AF. Both of these strategies are currently used to treat patients with persistent AF. However, no RCT has been

conducted to investigate which strategy is more efficacious. Primary outcome will be freedom from any documented atrial arrhythmia (including AF, atrial flutter, or tachycardia longer than 30 seconds) after one ablation procedure. Secondary endpoints will be freedom from atrial arrhythmia and after two ablation procedures, use of antiarrhythmic medication, procedure time, incidence of repeat procedures, and incidence of periprocedural complications.

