Figure 2. Three-dimensional electroanatomic map. Pulmonary vein and posterior wall ablation locations.

In both cases, a pace and ablate strategy will be completed around all lesions sets in a standard fashion. Isuprel will be employed to look for further AF, but will not be further ablated. If cavotricupid dependent typical flutter is seen, this will be ablated in either group.

Follow-up

Follow-up visits will occur either in doctors office or by phone at 1 month, 3 months, 6 months, and 1 year post ablation. Antiarrhythmic drugs (AAD) may be discontinued at 1 month if indicated. All patients would receive a continuously recording electrocardiogram (ECG) heart card to monitor for AF for the first month, and then two week ambulatory monitors at 3 months and one year post ablation.

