7.0 SPECIMEN/DATA COLLECTION/PROCEDURES

The investigators and study staff will obtain the necessary data during the ablation procedure, from electronic and paper medical records and monitoring devices. The information will be entered in a secure database with access limited only to study personnel. No specimens will be collected.

Data will be collected at baseline, during the ablation procedure and at each follow-up visit.

Baseline - Medical history, demographics, height, weight, BMI, cardiac medications, creatinine and 12-lead ECG.

Procedure - Ablation procedure details, medications administered, and adverse events.

Pre-discharge – Cardiac medications, arrhythmia events, adverse events.

Follow-up – In-Clinic/Telephone Visits -

The study requires total of 4 follow-up visits at (months 1, 3, 6 and 12) that can be completed either by telephone or in doctor's office. Telephone contact will last approximately 10 minutes each. Following assessments will be collected.

- Current concomitant medication documentation.
- ECG Recording – will be collected only if participant had ECG done at their own doctor's office or if the site has provided the ambulatory event monitor after the procedure to collect ECG recordings,
- Documentation of any adverse events/ serious adverse events occurring since the previous evaluation. All clinically significant adverse events should be carefully documented by the research staff using the adverse event data forms.

If a clinic visit occurs as part of the subject's regular medical care during the specified follow-up window, the follow-up assessment may be conducted during this visit, and no separate telephone contact is necessary.

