9.0 STATISTICAL CONSIDERATIONS

Demographics, baseline and treatment characteristics will be summarized for the study population. Descriptive statistics for baseline characteristics will be prepared for the two treatment groups for all randomized subjects. Continuous variables will be summarized using the number of subjects with data (n), mean, standard deviation, median, minimum and maximum. Chi-square statistics and Wilcoxon rank sum tests will be used to evaluate baseline differences between the arms for categorical and continuous variables respectively.

An interim data analysis will be performed after 40 subjects are enrolled.

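### The primary outcome is defined twice: section 1.0 requires patients to be off antiarrhythmic drugs, section 3.0 does not, and nothing says which governs

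*Protocol*

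**What the plan says.** The protocol states its primary outcome in two places.

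- Section 1.0 (Abstract, Expected Outcomes): "Primary study outcome is the percentage of patients free from atrial arrhythmias and off AADs at 1 year after single ablation procedures".
- Section 3.0 (Objectives/Study Aims): "Primary outcome will be freedom from any documented atrial arrhythmia (including AF, atrial flutter, or tachycardia longer than 30 seconds) after one ablation procedure". The secondary endpoints listed in the same section include "use of antiarrhythmic medication, procedure time, incidence of repeat procedures, and incidence of periprocedural complications".

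Three other places bear on the point.

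- Section 6.0 (Follow-up) leaves AAD withdrawal optional: "Antiarrhythmic drugs (AAD) may be discontinued at 1 month if indicated". The last of the four scheduled contacts is at 1 year.
- Section 7.0 lists, for every follow-up contact, "Current concomitant medication documentation".
- Section 9.0 neither restates the primary outcome nor says which definition applies. It does state: "An interim data analysis will be performed after 40 subjects are enrolled".

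**The concern.** The two statements can classify the same patient differently. Section 1.0 counts a patient as a success only if free of arrhythmia and also off AADs. Section 3.0 asks about rhythm alone. One estimates an effect on drug-free success, the other an effect on rhythm whatever the drug treatment.

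The protocol therefore does not fix which result answers its main question. An analysis that follows one section contradicts the other, and either result could later be presented as the protocol's primary. If the choice were made after outcomes by arm had been seen, the data could influence it.

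**Working it through.** **Comparing the two statements**

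| Element | Section 1.0 | Section 3.0 |
|---|---|---|
| Off AADs required | Yes | Not stated; AAD use is a secondary endpoint |
| Assessment time | 1 year | Not stated |
| 30-second threshold | Not stated | Stated |
| Number of procedures | One | One |

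Neither statement contains the other. The decisive row is the first. A patient with no documented arrhythmia through 1 year who is still on an AAD is a failure under 1.0 and a success under 3.0. Because withdrawal is optional under section 6.0, such patients can occur.

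Timing is a lesser matter. Follow-up ends at 1 year, so that horizon can be inferred for 3.0. Within 1.0, the time reference could mean status at 1 year or freedom up to 1 year.

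**Illustrating the size**

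The protocol has no figure to reproduce here: it gives no expected arrhythmia-free rate, AAD rate or effect. The one input taken from it is 50 patients per arm (section 6.0). Every rate below is an assumption.

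Let p1 and p2 be the arrhythmia-free proportions in Arms 1 and 2, and a1 and a2 the proportions of those patients still on an AAD at 1 year.

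- Difference under 3.0 = p2 − p1
- Difference under 1.0 = p2(1 − a2) − p1(1 − a1)
- Patients reclassified = 50·p1·a1 + 50·p2·a2

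Take p1 = 0.60 and p2 = 0.75. Under 3.0 the difference is 0.75 − 0.60 = 0.15, or 15 points. Under 1.0:

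| a1 / a2 | Arm 1 | Arm 2 | Difference (points) | Reclassified of 100 |
|---|---|---|---|---|
| 5% / 5% | 0.60 × 0.95 = 0.570 | 0.75 × 0.95 = 0.7125 | 14.3 | 1.5 + 1.9 = 3.4 |
| 15% / 15% | 0.60 × 0.85 = 0.510 | 0.75 × 0.85 = 0.6375 | 12.8 | 4.5 + 5.6 = 10.1 |
| 30% / 30% | 0.60 × 0.70 = 0.420 | 0.75 × 0.70 = 0.525 | 10.5 | 9.0 + 11.25 = 20.3 |
| 15% / 30% | 0.510 | 0.525 | 1.5 | 4.5 + 11.25 = 15.8 |
| 30% / 15% | 0.420 | 0.6375 | 21.8 | 9.0 + 5.6 = 14.6 |

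With equal use a in both arms, the difference is (1 − a)(p2 − p1), so it shrinks but keeps its direction. With 15% use in Arm 1, it reaches zero when Arm 2 use is 1 − 0.510/0.75 = 0.32. Nothing in the protocol says use will differ by arm; the unequal rows only show the range.

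**A second set of assumed rates**

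Take 55% and 75% arrhythmia-free, 50 per arm and two-sided 5% significance. Power is approximated by Φ{[d − 1.96·√(2·p̄(1 − p̄)/50)] / √([q1(1 − q1) + q2(1 − q2)]/50)}. Here q1 and q2 are the success rates under the definition used, d is their difference and p̄ their mean.

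- Under 3.0: d = 0.20 and p̄ = 0.65, so the argument is (0.20 − 0.187)/0.0933 = 0.14 and power is about 56%.
- Under 1.0 with 10%, 20% or 30% AAD use in both arms: differences of 18, 16 and 14 points, with power of about 45%, 36% and 29%.

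The conclusion is the same: the definition changes both the estimate and the chance of detecting a difference.

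**The case against.** The strongest counter-argument is that the two statements complement each other. On this reading the abstract supplies AAD status and the horizon, and section 3.0 supplies the rhythm definition and threshold. Section 3.0 does not say that AAD use is to be ignored, and the wording of its secondary endpoints is loose enough to suggest hasty drafting rather than a deliberate second definition. This does not rescue the text. A summary may leave out detail, but here it adds a condition for success that the objectives section lacks. A reader working from 3.0 would have no reason to apply it.

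Several narrower objections do stand, and they limit the finding.

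- The missing time in 3.0 is an omission, not a conflicting value, and 1 year can be inferred.
- A component of a primary outcome may also be reported as a secondary endpoint. Listing AAD use there supports the natural reading of 3.0 but proves nothing alone.
- All the rates are assumed. The most striking differences come from unequal AAD use, which nothing in the protocol predicts.
- Section 9.0 does not say that the interim analysis will examine the primary outcome. It is triggered by enrolment, so recently enrolled patients would not yet have 1-year data.

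It can also be said that the SAP, not available here, may settle the matter. But this is not detail left for later. The protocol itself states the primary outcome twice with different content, and a SAP that follows one statement leaves the other contradicted.

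**Conclusion.** The concern holds and must be fixed. The contradiction is the AAD condition, which is established from the protocol's wording alone and depends on no assumed rate. The assessment time and the meaning of the 1-year reference are secondary points that the same correction can settle.

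The number of patients affected cannot be known from the protocol. With 60% and 75% assumed arrhythmia-free and equal AAD use of 5% to 30% among them, about 3 to 20 of 100 patients are reclassified and the difference falls from 15 points to between 14.3 and 10.5. If AAD use differed by arm, the difference could be far smaller or larger: 1.5 and 21.8 points in the two cases shown.

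**What to change.** Reconcile sections 1.0 and 3.0 into one definition, worded identically in both. It should state:

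- whether being off AADs is part of the primary outcome;
- whether the outcome is status at 12 months or freedom through 12 months;
- the 30-second threshold.

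Report the other version as a named secondary endpoint. Either version is acceptable statistically. The choice belongs to the sponsor and investigator, and no change to AAD care is asked for. Settle it before any outcome data are reviewed, including at the interim analysis after 40 subjects.

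The cost is a one-sentence amendment in two sections. Arrhythmia recordings and concomitant medications are already collected at follow-up (sections 6.0 and 7.0), so both versions can be reported without new data.

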2.0 BACKGROUND/RATIONALE

Background

Atrial fibrillation (AF), the most common type of arrhythmia in clinical practice, affects approximately 2.7 million US adults. This number is expected to double over the next 25 years. AF accounts for 500,000 hospitalizations and 100,000 deaths annually and contributes to 15% of all strokes, the leading cause of death from AF, in the US. Caring for patients with AF is also expensive, costing approximately \$26 billion annually. An effective management strategy to mitigate AF is critical.

Pulmonary vein isolation (PVI) has emerged as the gold standard for management of paroxysmal AF with excellent success rates. A number of randomized controlled trials (RCTs) demonstrated superior efficacy of PVI by comparing it to drugs alone. In addition, although there are currently no prospective data to support this, retrospective data suggested that successful ablation seems to reduce stroke risk in patients with AF.

For patients with persistent AF, however, procedural efficacy from PVI is not optimal. Therefore, improved ablation strategies for these patients are needed.

Safety and efficacy data reviewed from our clinical practice over the last 10 years of two PVI ablation strategies, PVI alone and PVI plus posterior wall isolation, did not favor either technique currently used by our physicians, not suggest harm, and so we feel there is equipoise presently between the techniques.

3.0 OBJECTIVES/STUDY AIMS

The objective of this RCT is to compare 2 ablation strategies, PVI alone and PVI plus posterior wall isolation, in patients with persistent AF. Both of these strategies are currently used to treat patients with persistent AF. However, no RCT has been

conducted to investigate which strategy is more efficacious. Primary outcome will be freedom from any documented atrial arrhythmia (including AF, atrial flutter, or tachycardia longer than 30 seconds) after one ablation procedure. Secondary endpoints will be freedom from atrial arrhythmia and after two ablation procedures, use of antiarrhythmic medication, procedure time, incidence of repeat procedures, and incidence of periprocedural complications.

4.0 ELIGIBILITY

Inclusion Criteria:

1. Patients 18 years of age or older.
2. Have symptomatic persistent AF (i.e., a sustained episode lasting more than 7 days).
3. Undergoing ablation for the first time.

Exclusion criteria:

1. Paroxysmal AF
2. Sustained atrial fibrillation lasting more than 3 years
3. Left atrial diameter of 60 mm or greater
4. Severe Pulmonary hypertension

5.0 SUBJECT ENROLLMENT

Consecutive eligible patients will be approached in the clinics of the investigators. Informed consent shall be obtained in writing and documented in accordance with the principles of Informed Consent, according to Good Clinical Practice.

6.0 STUDY DESIGN/PROCEDURES

Randomized study of 100 participants into groups of 50 to undergo a radiofrequency ablation procedure for AF (defined below).

Procedure

For both groups, a standard approach by our lab which has previously been described will be used. Briefly, general anesthesia will be provided by an anesthesiologist. A TEE will be done to confirm no left atrial appendage thrombus. The anesthesiologist will place a radial art line and place an esophageal temperature probe posterior to the left atrium to monitor esophageal temperatures during ablation on the posterior wall of the left atrium. The right groin catheter insertion site will be prepped and draped in sterile fashion. Local anesthesia will be used. An 8, 8, and long 9 French sheath will be placed percutaneously in to the right femoral vein utilizing ultrasound guidance and seldinger technique with visualization of vascular entry with the needle. A 20 pole deflectable catheter will be placed in the right atrium with the main body wrapped along the tricuspid valve annulus and tip in the proximal coronary sinus. An intracardiac ultrasound catheter will be used for transeptal access. The short 8 french sheath will then be exchanged over a long guidewire for a long 8.5 french transeptal sheath. A transseptal cardiac catheterization will be performed in standard fashion utilizing

intracardiac echo, fluoroscopic guidance, and hemodynamic monitoring. A Baylis RF needle will be used for transeptal puncture utilizing RF energy of 10 watts over 2 seconds. A heparin bolus will be administered immediately upon left atrial access followed by further boluses and a heparin drip through the transeptal sheath. ACT target will be 250. Serial ACT measurements will be made at least every 20 minutes. All sheaths will be flushed and maintained with heparinized saline. An electroanatomic map of the left atrium will be created using a circular mapping catheter (CMC) and a three dimensional mapping system. Radiofrequency ablation (RF) will be performed using a 3.5 mm irrigated force sensing catheter in power control mode. Force will be targeted for 10-20 grams 85% of the time. RF settings will be between 30-50 watts depending on the location of RF application. It is anticipated that the majority of RF ablation in the left atrium will be performed with 50 watts. Mapping will be performed fluoroscopically and electro-anatomically. Esophageal temperature will be monitored, and ablation discontinued if the temperature rises by 1 degrees Celsius. Rapid pacing will be performed in the left atrium with isoproterenol to induce atrial fibrillation and any organized arrhythmias. Any clinically relevant organized arrhythmias will be mapped and ablated. No specific trigger mapping will be performed unless patient is unconvertible due to immediate return of AF.

For Group 1, a series of RF applications will be delivered around both sets of pulmonary veins with complete entry and exit block obtained around the antrums of all 4 pulmonary veins (Figure 1).

[figure not shown]

Figure 1. Three-dimensional electroanatomic map. Pulmonary vein ablation locations.

For Group 2, a series of RF applications will be delivered around both sets of pulmonary veins with complete entry and exit block obtained around the antrums of all 4 pulmonary veins. Then, a roof and low posterior line will be placed to achieve entrance and exit block on the posterior wall. Entry block on the posterior wall will be confirmed by placing the circular mapping catheter in multiple locations along the posterior wall

and confirming lack of presence of any local potentials. Exit block will be confirmed on the posterior wall with pacing at 10 amps from the ablation catheter at multiple locations within the box as well as all lines (Figure 2).

[figure not shown]

Figure 2. Three-dimensional electroanatomic map. Pulmonary vein and posterior wall ablation locations.

In both cases, a pace and ablate strategy will be completed around all lesions sets in a standard fashion. Isuprel will be employed to look for further AF, but will not be further ablated. If cavotricupid dependent typical flutter is seen, this will be ablated in either group.

Follow-up

Follow-up visits will occur either in doctors office or by phone at 1 month, 3 months, 6 months, and 1 year post ablation. Antiarrhythmic drugs (AAD) may be discontinued at 1 month if indicated. All patients would receive a continuously recording electrocardiogram (ECG) heart card to monitor for AF for the first month, and then two week ambulatory monitors at 3 months and one year post ablation.

7.0 SPECIMEN/DATA COLLECTION/PROCEDURES

The investigators and study staff will obtain the necessary data during the ablation procedure, from electronic and paper medical records and monitoring devices. The information will be entered in a secure database with access limited only to study personnel. No specimens will be collected.

Data will be collected at baseline, during the ablation procedure and at each follow-up visit.

Baseline - Medical history, demographics, height, weight, BMI, cardiac medications, creatinine and 12-lead ECG.

Procedure - Ablation procedure details, medications administered, and adverse events.

Pre-discharge – Cardiac medications, arrhythmia events, adverse events.

Follow-up – In-Clinic/Telephone Visits -

The study requires total of 4 follow-up visits at (months 1, 3, 6 and 12) that can be completed either by telephone or in doctor's office. Telephone contact will last approximately 10 minutes each. Following assessments will be collected.

- Current concomitant medication documentation.
- ECG Recording – will be collected only if participant had ECG done at their own doctor's office or if the site has provided the ambulatory event monitor after the procedure to collect ECG recordings,
- Documentation of any adverse events/ serious adverse events occurring since the previous evaluation. All clinically significant adverse events should be carefully documented by the research staff using the adverse event data forms.

If a clinic visit occurs as part of the subject's regular medical care during the specified follow-up window, the follow-up assessment may be conducted during this visit, and no separate telephone contact is necessary.

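### The same study team obtains the procedure data and the arrhythmia recordings, and the protocol masks neither the patient nor the person who classifies the recordings; both could be masked at little cost

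*Protocol*

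**What the plan says.** Section 7.0 names who gathers the data: "The investigators and study staff will obtain the necessary data during the ablation procedure, from electronic and paper medical records and monitoring devices". The list that follows includes ablation procedure details, arrhythmia events before discharge, and the follow-up assessments.

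Section 3.0 defines the primary outcome as "freedom from any documented atrial arrhythmia (including AF, atrial flutter, or tachycardia longer than 30 seconds") after one procedure. The abstract (section 1.0) words it differently and adds a drug condition: "Primary study outcome is the percentage of patients free from atrial arrhythmias and off AADs at 1 year after single ablation procedures".

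Sections 6.0 and 7.0 allow every follow-up visit to take place by telephone. Section 7.0 says that an ECG recording "will be collected only if participant had ECG done at their own" doctor's office, or if the site supplied an ambulatory monitor. Section 6.0 schedules monitoring for all patients: a continuous recorder in the first month, then two-week monitors at 3 months and at one year.

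Section 6.0 describes a common procedure for both groups: "Briefly, general anesthesia will be provided by an anesthesiologist", followed by the same venous access, transseptal puncture and mapping. The arms differ in the added posterior-wall lesions and their testing.

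Masking of the patient, the follow-up staff or the reader of recordings is not mentioned in any section.

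**The concern.** An outcome that counts documented arrhythmia depends on how hard someone looks and on how a borderline recording is called. Three steps are open to influence by a person who knows the arm:

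- whether an extra ECG is sought between scheduled monitors, by the patient or by a doctor;
- what is reported and followed up in a short telephone contact;
- whether a run is judged to exceed 30 seconds.

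If these steps differ by arm, the primary comparison is biased. Analysis can reduce this, for example by restricting to scheduled monitors, but it cannot recover arrhythmia that was never recorded. Who is masked is a matter of trial conduct that belongs in a protocol, and a statistical analysis plan cannot supply it afterwards.

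The same knowledge bears on use of antiarrhythmic drugs (AADs), which is part of the primary outcome in the abstract and a secondary endpoint in section 3.0, and on repeat procedures.

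**Working it through.** **Step 1. What the text establishes.** Section 7.0 assigns the procedure data and the monitoring-device data to one group in one sentence. Procedure details reveal the arm. Nothing separates the two roles or removes the arm from the recordings. It follows that the protocol leaves classification open to someone who knows the arm. It does not follow that this will happen.

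**Step 2. How much follow-up is monitored alike.** Taking month 1 as 30 days, scheduled monitoring covers 30 + 14 + 14 = 58 of 365 days, about 16% of the year. Arrhythmia outside those windows enters the outcome only through unscheduled contact. The share of recurrences found by the scheduled monitors may be much larger than 16%, because recurrent arrhythmia can persist or repeat. The protocol gives no figure for it.

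**Step 3. Size under assumptions.** The protocol gives no figure to reproduce on this point. Its only input is 50 patients per arm (section 6.0). Everything else is assumed:

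- true 1-year recurrence r, equal in both arms: 40% or 50%;
- share e of recurrences detected in both arms alike by scheduled monitoring: 0, 0.5 or 0.7;
- detection of the remainder: 75% v 65%, or 80% v 60%;
- test: two-sided 5% chi-square without continuity correction. The protocol names chi-square only for baseline comparisons, so the test too is an assumption.

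Observed recurrence in an arm = r × [e + (1 − e) × d], where d is that arm's detection of the remainder. The rejection rate is the exact binomial sum over all outcomes at 50 per arm.

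Example: r = 0.40, e = 0.5, d = 0.80 v 0.60. Observed recurrence is 0.40 × (0.5 + 0.40) = 0.36 against 0.40 × (0.5 + 0.30) = 0.32, a false difference of 4 points.

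| r | e | d | Observed recurrence | False difference | Rejection rate |
|---|---|---|---|---|---|
| 40% | 0 | 75% v 65% | 0.30 v 0.26 | 4 points | 7.3% |
| 40% | 0 | 80% v 60% | 0.32 v 0.24 | 8 points | 14.5% |
| 40% | 0.5 | 75% v 65% | 0.35 v 0.33 | 2 points | 5.4% |
| 40% | 0.5 | 80% v 60% | 0.36 v 0.32 | 4 points | 6.9% |
| 40% | 0.7 | 75% v 65% | 0.370 v 0.358 | 1.2 points | 5.2% |
| 40% | 0.7 | 80% v 60% | 0.376 v 0.352 | 2.4 points | 5.7% |
| 50% | 0 | 75% v 65% | 0.375 v 0.325 | 5 points | 8.1% |
| 50% | 0 | 80% v 60% | 0.40 v 0.30 | 10 points | 18.0% |

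With equal detection the rate stays near nominal: 5.0% to 5.7% for recurrence of 30% to 50% when all recurrences are detected.

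**Step 4. Scale.** With 80% power at 50 per arm, the detectable difference is about 22 points when freedom from arrhythmia in the control arm is 70%, rising to about 28 points when it is 40%. A false difference of 1 to 5 points is small against that. One of 8 to 10 points is not.

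**The case against.** The strongest reply is that the quoted sentence is a general statement of data sources. A reader might infer that the operators themselves judge the outcomes. The protocol does not say so. It says that patients are approached in the investigators' clinics ("Consecutive eligible patients will be approached in the clinics of the investigators") and that the site's past data "did not favor either technique currently used by our physicians", which suggests overlap between operators and investigators. But section 7.0 also names study staff and gives adverse-event documentation to research staff. Nor does the protocol declare the trial open-label; it is silent on masking. What patients are told about their arm might stand in the consent form, which was not available for this review. These points stand, and the concern is confined to what the text leaves open.

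Second, monitoring is scheduled identically for all patients. This also stands, and it is why the rows with e = 0 are upper-range scenarios. It does not settle the matter: the windows are short, and identical monitors do not mask the person who reads them.

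Third, one might read the table as evidence that one arm will be favoured. It is not. The detection rates are invented for illustration, and the background section claims equipoise.

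Fourth, a masked reader addresses only classification, the most objective step, while drug withdrawal, repeat ablation and physician-ordered ECGs stay with physicians who may know the arm. This is correct and limits what the fix can achieve. Withholding the arm from the patient does reach symptom reporting and patient-initiated ECGs.

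Last, general anesthesia in both arms might suggest that patient masking is free. It is feasible at little cost, but charts and conversations after the procedure would need control.

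**Conclusion.** The concern holds in a limited form. The protocol puts arm-revealing procedure data and outcome recordings in the same hands, masks neither the patient nor the reader, and uses an outcome that depends on documentation. That leaves room for detection to differ by arm, in a direction that the document cannot show. Under the assumed gaps, the false-positive rate is about 5% to 7% at 40% recurrence if at least half of recurrences are detected equally. It reaches 14.5% at 40% recurrence and 18.0% at 50% only if the gap is 80% v 60% and applies to every recurrence. These figures rest on assumed recurrence, detection and test; they illustrate the risk and do not estimate it. This is a cheap improvement and does not show that the comparison is invalid.

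**What to change.** Add two statements:

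- **Section 6.0:** the assigned lesion set is not disclosed to the patient until the month-12 assessment is complete, unless clinically needed.
- **Section 7.0:** all monitor and ECG recordings used for the primary outcome are labelled by study number only, and are classified against the 30-second rule by an existing team member who did not perform that patient's procedure and does not see the arm.

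Also acknowledge as a limitation that treating physicians are not masked, so AAD use (part of the abstract's primary outcome), repeat ablation and physician-ordered ECGs remain open to influence.

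The cost is two sentences and coded labels, with no new staff, visits or tests. The downside is that the procedure report must be kept from the reader, and some patients may learn their arm anyway.
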